### **7.3. Variables**

#### **7.3.1. Exposure definitions**

##### **Veterans without HIV (Objective 1a)**

Not applicable

##### **Veterans with a new HIV diagnosis (Objective 1a)**

PrEP use (never, ever: use within  $\leq 12$  months before diagnosis, use  $> 12$  months before diagnosis)

##### **Veterans who could benefit from PrEP (Objective set 2)**

Not applicable

##### **Veterans initiating a PrEP regimen during the study period (Objective set 3)**

PrEP type (oral TDF/FTC, oral TAF/FTC or CAB LA).

#### **7.3.2. Baseline characteristics**

The following variables will be assessed for objectives 2.1 and 3.1 at index date:

- **Demographic characteristics**

- Age (years)
- Birth sex
- Race (American Indian or Alaska Native, Asian, Black or African American, Native Hawaiian or Pacific Islander, White, Not reported)
- Ethnicity (Hispanic, not Hispanic)
- Geographic Region (Northeast, Midwest, South, West, US Territories)
- Rurality (Highly rural, Rural, Urban)
- Marital/Relationship status
- Homelessness in the past 12 months

- **Clinical characteristics**

- Number of outpatient visits in the 12 months prior to index date
- Number of primary care outpatient visits in the 12 months prior to index date
- Comorbidity burden using the Charlson Comorbidity Index
- PrEP prescriber specialty
- Psychiatric diagnoses (major depression, bipolar disorder, post-traumatic stress disorder - PTSD, schizophrenia)
- Substance use (smoking, alcohol use disorder, injection and non-injection illicit drug use disorder)
- BMI

- VACS Index 2.0
- **Sexual Behavior and Health**
  - History of STI (ever)
    - Syphilis
    - Gonorrhea
    - Chlamydia
    - Chancroid
    - Lymphogranuloma venereum
    - *Mycoplasma genitalium*
    - Hepatitis B virus (HBV)
    - Hepatitis C virus (HCV)
    - Genital herpes – Herpes Simplex Virus (HSV) 1 or 2
    - Trichomoniasis infection
    - Genital Human papilloma virus (HPV) including warts
  - History of STI (past 3 months)
    - Syphilis
    - Gonorrhea
    - Chlamydia
    - Chancroid
    - Lymphogranuloma venereum
    - *Mycoplasma genitalium*
    - Hepatitis B virus (HBV)
    - Hepatitis C virus (HCV)
    - Genital herpes
    - Trichomoniasis infection
    - Genital Human papilloma virus (HPV) including warts
  - History of PrEP use

### 7.3.3. Outcome definitions

#### ◆ Veterans without HIV (Objective 1)

Incident HIV diagnosis: a new HIV diagnosis is defined as either having a (1) positive screening antibody test with positive confirmatory antibody testing, (2) positive HIV viral load, or (3) documentation of HIV on the EHR problem list.

All potential HIV incident diagnosis will be subject to a detailed review for confirmation.

#### ◆ People with a new HIV diagnosis (Objective 1.a)

Not applicable

#### ◆ People without HIV who are not on PrEP and could benefit from PrEP (Objective set 2)

##### ◆ HIV testing & STI screening (Objective 2.2)

- HIV testing
  - Frequency and rate of HIV tests over 12-month period following the index date

- Type of HIV tests
- HIV diagnoses
  - Frequency and rate of new HIV diagnosis within 12 months of index date (first visit with at least one criteria for PrEP)  
Follow-up (FU) will be censored at first of:
    - HIV diagnosis
    - 12 months after index date
    - End of the study period
    - Loss to follow-up
    - Death
- STI testing/screening
  - Frequency and rate of STI testing events, overall (testing for multiple STIs on the same day will count as 1 testing event) and by type of STI tested  
Type of STI:
    - Syphilis
    - Gonorrhea
    - Chlamydia
    - Chancroid
    - Lymphogranuloma venereum
    - *Mycoplasma genitalium*
    - Hepatitis B virus (HBV)
    - Hepatitis C virus (HCV)
    - Genital Herpes (HSV-1, HSV-2)
    - Trichomoniasis
    - Genital Human papilloma virus (HPV) including warts  
Follow-up (FU) will be censored at first of:
    - HIV diagnosis
    - 12 months after index date
    - End of the study period
    - Loss to follow-up
    - Death
- STI diagnoses
  - Frequency and rate of new diagnosis of STI as noted in medical record or positive test result
  - STI diagnoses for
    - Syphilis
    - Gonorrhea
    - Chlamydia
    - Chancroid
    - Lymphogranuloma venereum
    - *Mycoplasma genitalium*
    - Hepatitis B virus (HBV)
    - Hepatitis C virus (HCV)
    - Genital Herpes (HSV-1, HSV-2)
    - Trichomoniasis

- Genital Human papilloma virus (HPV) including warts

◆ **PrEP users (Objective set 3)**

◆ **Use of oral lead-in (Objective 3.2)**

CAB PrEP formulation at initiation: proportion with CAB oral lead-in (OLI) vs. direct to injection (DTI)

◆ **Adherence (Objective 3.3)**

**a) Oral PrEP coverage in the 12 months following initiation**

PrEP dispensing is considered as a proxy for PrEP use. The number of dispensing events will be described.

The number of pills dispensed/days covered per dispensing event will be calculated.

Proportion of days of access to oral PrEP in the 12 months following index PrEP initiation

Follow-up (FU) will be censored at first of:

- 12 months after index date
- Loss to follow-up
- Death
- Study end

**b) Adherence to CAB LA PrEP schedule**

- Proportion of days covered by CAB LA PrEP in the 12 months following initiation: number of days covered by CAB LA PrEP divided by the number of days in the observation period

Follow-up will be censored at first of:

- a) 12 months after index date
- b) Loss to follow-up
- c) Death
- d) Study end

Coverage by LA PrEP will be determined based on the duration of days covered by the medication, according to the label.

- 1st injection: coverage = 37 days (30 days of coverage + 7-day injection window)
- Subsequent injections: coverage = 67 days (60 days of coverage + 7-day injection window)

Each calendar day will only be counted once, even if there is an overlap between coverage from the prior injection and date of the next injection.

- **Complete versus incomplete initiation:**

- Among all Veterans with  $\geq 1$  CAB LA injection:

→ Complete initiation (2nd injection received within 67 days following the 1st injection)

- 2nd initiation injection on time: 2nd injection between 23 and 37 days following the first injection
- 2nd initiation injection late: 2nd injection between 38 and 67 days following the first injection

→ Incomplete initiation: >67 days without injection following the first injection

- Among incomplete initiators

Any additional injection(s) >67 days after the 1st injection (Yes/no)

If yes:

- o Timing of the 1st additional injection after the last injection of the “incomplete initiation” (interval in days, number with interval of 68-97 days and interval >97 days)
- o Complete versus incomplete reinitiation
- o Interval between the first two reinitiation injections ( $\leq 37$ ; 38-67, 68-97, 98-127;  $\geq 128$  days apart)

• **Timing of CAB LA PrEP maintenance injections:** among complete initiators with at least one maintenance injection

Determined based on the time between initiation injections (Table 3)

- Total number of maintenance injections per individual
- All on time
- Any late maintenance injection (short delays not requiring reinitiation, long delays requiring reinitiation): number of short and long delays, number of individuals with 1, 2, 3 or more short delays, number of individuals with 1, 2, 3 or more long delays, median duration of short and of long delays

**Table 3:** Timing of CAB LA PrEP maintenance injections, among complete initiators with  $\geq$  maintenance injection

Dosing pattern	Timing of maintenance injections (following previous injection)
On-time	53-67 days
Late	68-127 days
Short delay not requiring reinitiation	68-97 days
Long delay requiring reinitiation	98-127 days
Discontinuation	>127 days without injection

◆ **Patterns of PrEP use (Objective 3.4)**

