## **7. RESEARCH METHODS**

### **7.1. Study Design**

This is a cohort study using data from the Veterans Affairs National Sample, which is composed of Veterans who receive healthcare services through the Veterans Health Administration (VHA). This national sample is representative of the Veteran population, capturing a wide range of demographic, clinical, and social characteristics.

Data will be extracted from VHA's Corporate Data Warehouse (CDW), a comprehensive, regularly updated repository of information from VHA's electronic health records and administrative files. It includes patient-level data such as demographics, clinical encounters (diagnoses, interventions), laboratory and imaging results, medication details, health services utilization, and long-term health outcomes.

The study period will range from January 1, 2021, to December 31, 2025. Initiation of PrEP regimen will be assessed during the period January 1, 2021 to June 30, 2025, to allow for at least 6 months of observation following PrEP initiation.

The study will include different cohorts, as described in Table 2.

Veterans who are not on PrEP but could benefit from PrEP will be identified based on risk factors for HIV acquisition or factors linked to behaviors increasing the risk of HIV acquisition which are generally documented in Veterans health records. These risk factors include: tested for or diagnosed with a bacterial STI in the past 12 months (gonorrhea, syphilis, chlamydia) (US CDC, 2024), tested for HIV in the past 12 months, ever had alcohol use disorder (Williams, 2016), ever used illicit non-injection drugs (HIV.gov, 2024), ever used injectable drugs (CDC, 2024), Black women (CDC, 2024; Reaves, 2025), men who have sex with men (CDC, 2022; Mayer, 2021), individuals aged 18-24 years (HIV.gov, 2025 b), any history of PrEP use (Hojilla, 2021; Krakower, 2019).

---

 The US CDC recommends PrEP for people with a bacterial STI diagnosis in the past 6 months. This has been extended to testing for a bacterial STI in the past 12 months for this protocol.

**Table 2:** Description of study cohorts

Objectives	Criteria	
Objective 1a - Among all Veterans without evidence of HIV infection	Population/exposure	No evidence of HIV diagnosis at beginning of each calendar year of the study period under analysis
	Index date	N/A
	Censoring criteria	N/A
	Endpoint	HIV diagnosis

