## 7.2. Study Population and Setting

### 7.2.1. Inclusion criteria

- **Veterans in care without evidence of HIV infection (Obj. 1.1)- individuals will be included if they meet all of the following criteria:**

- At least one VHA health encounter in the calendar year
- $\geq 18$  years of age
- No evidence of HIV infection at the beginning of the calendar year under analysis

- **Veterans in care with a new HIV diagnosis (Obj. 1.2):**

- Incident HIV diagnosis (refer to definition in section 7.3.3)

- **Veterans in care without evidence of HIV infection who are not on PrEP but who could benefit from PrEP (Objective set 2)- individuals meeting all of the following criteria:**

- At least one VHA health encounter during the study period
- $\geq 18$  years of age
- Any of the following criteria indicating that the individual has a risk factor for HIV acquisition or a factor linked to behaviors increasing the risk of HIV acquisition and may benefit from PrEP:
  - tested for or diagnosed with a bacterial STI in the past 12 months (gonorrhea, syphilis, chlamydia),
  - tested for HIV in the past 12 months,
  - ever had alcohol use disorder,
  - ever used illicit non-injection drugs,
  - ever used injectable drugs,
  - Black women,
  - men who have sex with men,
  - individuals aged 18-24 years,
  - any history of PrEP use
- No evidence of HIV infection at the first health encounter with a criteria for PrEP

- **Veterans in care using oral PrEP only (objective set 3)**

- At least one VHA health encounter during the study period
- $\geq 18$  years of age
- Received at least one oral PrEP prescription (TDF/FTC, TAF/FTC) between January 1 2021 and 31 December 2024
- No evidence of HIV infection at the time of the first oral PrEP prescription in the study period
- Have not received a CAB LA PrEP injection between January 1, 2021, and June 30, 2025

- **Veterans in care using CAB LA for PrEP (objective set 3)**

- At least one VHA health encounter during the study period
- $\geq 18$  years of age
- Received at least one CAB LA PrEP injection between January 1, 2021 and June 30, 2025

- No evidence of HIV infection at the time of the first CAB LA PrEP injection in the study period

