##### **Veterans using PrEP (Objective set 3)**

**Objective 3.1-** Baseline demographic and clinical characteristics will be described at the start of PrEP use during the study period, by regimen type (oral or CAB LA), using median and interquartile ranges for continuous variables and counts and proportions for categorical variables.

**Objective 3.2-** The proportions of Veterans on care initiating CAB LA PrEP who used oral lead in (OLI) and proportion of those with direct to injection (DTI) will be calculated.

**Objective 3.3 and 3.4-** PrEP adherence and usage patterns will be described using median and interquartile range for continuous data as well as absolute and relative frequencies for categorical data. The percentage of days with access to oral PrEP and CAB LA PrEP will be described over the first 12 months after index PrEP initiation. Characteristics of individuals with and without delayed CAB LA injections as well as individuals with and without discontinuation will be compared using Pearson's chi-square tests for categorical variables and Mann-Whitney tests for continuous variables.

**Objective 3.5-** Incidence rates and confidence intervals for HIV testing, HIV diagnosis, STI testing/screening and STI diagnosis will be calculated using univariate Poisson regression. STI treatment prescription will be described using absolute and relative frequencies for categorical data.

**Objective 3.6-** For CAB LA PrEP users diagnosed with HIV, a timeline including details of oral PrEP prescriptions prior to CAB LA PrEP start, injections received, HIV tests performed, HIV treatment, viral load measurements, HIV drug resistance will be provided for each individual.

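### The 12-month proportion of days covered for CAB LA pools observation windows of 184 to 365 days, and the conflicting oral entry dates leave open whether oral PrEP is affected too

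*Protocol*

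**What the plan says.** Section 7.3.3 of the Protocol, under adherence to the CAB LA schedule, reports "Proportion of days covered by CAB LA PrEP in the 12 months following initiation", calculated as "number of days covered by CAB LA PrEP divided by the number of days in the observation period". Follow-up stops at the first of 12 months after index, loss to follow-up, death and study end. Table 2 repeats these rules and places loss to follow-up 12 months after the last clinical contact. Section 7.3.3 gives oral PrEP coverage the same four stopping points. Section 7.7.1.1 states that the percentages for oral and CAB LA PrEP "will be described over the first 12 months after index PrEP initiation", summarised by median and interquartile range.

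The calendar is set in two places that do not agree for oral PrEP:

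- Section 7.1: "The study period will range from January 1, 2021, to December 31, 2025". For PrEP without distinction of modality: "Initiation of PrEP regimen will be assessed during the period January 1, 2021 to June 30, 2025", which is meant "to allow for at least 6 months of observation following PrEP initiation".
- Section 7.2.1, CAB LA users: "Received at least one CAB LA PrEP injection between January 1, 2021 and June 30, 2025". Oral-only users: "Received at least one oral PrEP prescription (TDF/FTC, TAF/FTC) between January 1 2021 and 31 December 2024".

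The Synopsis (Study Size) and section 7.5 count 15,477 oral and 748 CAB LA users, both to 30 June 2025.

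**The concern.** A proportion of days covered depends on the length of the window when people stop treatment. A person who stops early keeps the same covered days, while the denominator grows with the window. If the most recent CAB LA entrants are scored over 6 to 12 months and everyone else over 12, part of the reported level reflects when the data were cut and not how people used the injections. A reader will take the result as a 12-month quantity, which it is not for those entrants.

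The protocol says in section 5 that recent adherence data, including for long-acting injectable PrEP, are lacking, so these figures are likely to be quoted. The oral and CAB LA percentages also carry the same 12-month label, which invites reading them together. Whether they share the same distortion turns on which oral entry date applies.

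**Working it through.** **Plan's own figure.** Table 4 uses p ± 1.96·√(p(1−p)/N). With p = 0.8 and N = 748: 1.96·√(0.16/748) = 0.0287, giving 0.771 to 0.829. This matches the stated 77–83%.

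**Step 1: windows** (dates from 7.1 and 7.2.1, counting days after index). 30 June 2025 to 31 December 2025 is 184 days. 1 January 2025 to 31 December 2025 is 364 days. 31 December 2024 to 31 December 2025 is 365 days. So CAB LA users indexed from 1 January to 30 June 2025 have 184 to 364 days. If the first injection counts as a clinical contact, loss to follow-up cannot fall before 12 months; only death or study end can then shorten the window.

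**Step 2: same user, two windows.** Section 7.3.3 gives 37 days of coverage to the first injection and 67 to each later one. With injections on days 0, 30, 90, 150 and so on, coverage ends at day 37, 30 + 67 = 97, 90 + 67 = 157 or 150 + 67 = 217 for a user who stops after one, two, three or four injections.

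| Stops after injection | 184-day window | 365-day window |
|---|---|---|
| 1 | 37/184 = 20.1% | 37/365 = 10.1% |
| 2 | 97/184 = 52.7% | 97/365 = 26.6% |
| 3 | 157/184 = 85.3% | 157/365 = 43.0% |
| 4 | 184/184 = 100% | 217/365 = 59.5% |
| never | 100% | 100% |

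This step assumes on-schedule injections but nothing about accrual or persistence.

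**Step 3: share of CAB LA users affected** (entry pattern assumed). The late period is 180 days of an entry span of about 1,641, 1,276 or 1,095 days (first entry January 2021, January 2022 or July 2022). Uniform entry gives u = 180/span = 11%, 14% or 16%. Linearly rising entry gives 1 − (1 − u)² = 21%, 26% or 30%. Of 748, that is about 82 to 226 users.

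**Step 4: effect on the mean** (persistence assumed). Let the stopping probability p after each injection be constant. A 365-day window holds seven scheduled injections, so 12-month persistence is (1 − p)⁶. Late windows are spread evenly over 184 to 364 days.

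| 12-month persistence | Mean, 365 days | Mean, late windows | Excess |
|---|---|---|---|
| 40% | 66.4% | 73.7% | 7.2 points |
| 60% | 78.9% | 83.8% | 5.0 points |
| 85% | 92.5% | 94.4% | 1.9 points |

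The pooled shift is the late share times the excess: 0.11 × 1.9 = 0.2 points at the low end and 0.31 × 7.2, about 2.2 to 2.3 points, at the high end (31% is just above the top of Step 3).

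**Step 5: effect on the planned summary.** In the same model the median stays at 100% when persistence is above 50%. At 40% it moves by 0 to about 6.5 points. The lower quartile does not move at 60% or 85% persistence, but at 70% it can jump from 75.9% (277/365) to 92.3% (337/365), about 16 points. Such jumps partly reflect the few values that an exact schedule allows. A simulation with injection dates varying around the schedule (SD 5 days) gave at most about 4 points.

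**Step 6: the oral cohort.** Under 7.2.1 the last oral entrant has 365 days, so study end shortens no oral window. Under 7.1, and under the period used for the 15,477, the last oral entrant has 184 days, as for CAB LA. Section 7.3.3 lists study end as a stopping point for oral coverage, which would have no effect if 7.2.1 governs.

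**The case against.** The strongest reply is that nothing is hidden. The measure is a ratio over observed time, capped at 12 months; study end is a listed censoring event; and section 7.1 says openly that the design secures at least 6 months. Objective 3.3 names only the observation period, and objective 3.1 reports duration of follow-up. This stands, so a reader should not infer that the protocol promises every user a full 12 months. It does not, however, make a 184-day ratio and a 365-day ratio comparable, and nothing in the protocol separates them.

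A reader might also infer that the plan favours CAB LA over an oral cohort that always has 12 months. The documents do not support this. It holds only under 7.2.1 and apart from deaths; under 7.1 and the study-size counts both modalities are truncated alike. No test of oral against CAB LA adherence is planned, the study is stated to be descriptive, and section 7.9 already warns that oral dispensing is only a proxy for use.

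The effect on the planned median is often nil, and the upward shift is zero if nobody stops. That stands too and limits the weight of the point. Finally, a restricted analysis could be left to an analysis plan. But the entry dates, the denominator and the censoring rule are fixed in this protocol, and the contradiction over oral entry can be settled only there.

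**Conclusion.** The point holds in a limited form. Under the rules as written, the CAB LA figure labelled 12-month mixes windows of 184 to 365 days, and it is raised whenever users stop over time. Late entrants' mean is about 2 to 7 points too high and the pooled mean about 0.2 to 2.3 points, against a Table 4 half-width of 2.9 points at 80%. The lower quartile is the planned statistic most exposed, but its shift is unstable across assumptions; the median often does not move. These sizes rest on assumed persistence of 40 to 85% at 12 months and assumed late shares of about 11 to 31%, since the protocol gives neither. The direction and the same-user comparison do not depend on those assumptions.

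Whether oral PrEP is also affected cannot be settled from the protocol until the two entry dates are reconciled. Either way, at least the CAB LA figure is mislabelled for late entrants. This is a worthwhile and cheap improvement, not a flaw that invalidates the study.

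**What to change.** 1. Reconcile the end of oral PrEP entry across section 7.1, section 7.2.1 and the study-size text in the Synopsis and 7.5. If the earlier date is kept, recount the 15,477 to that date.
2. In 7.3.3, Table 2 and 7.7.1.1, calculate the 12-month proportion of days covered, in both modalities, only in users indexed on or before 31 December 2024. Study end then shortens no window, whichever oral date is chosen.
3. Add a 184-day proportion of days covered for all users in both modalities, which every permitted index date can supply.

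The cost is a few sentences and one extra row per modality, with no new data. About 11 to 30% of CAB LA users (assumed) leave the 12-month figure but stay in the 184-day one, so about 522 to 666 of 748 remain. The 95% half-width at 80% grows from 2.9 points to 1.96·√(0.16/666) = 3.0 or 1.96·√(0.16/522) = 3.4 points. The 12-month figure will no longer describe the most recent starters, and the report should say so.

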  - Proportion of CAB LA PrEP users with at least one maintenance injection who are on CAB LA PrEP at 12 months and 24 months after initiation and at the end of the study period
- 3.5- Described patterns of HIV and other STI testing/screening, diagnosis and STI treatment
- a) Assess the incidence of HIV testing and HIV diagnosis during the first period of PrEP use by PrEP modality
  - b) Estimate the frequency of testing for STI diagnosis and STI diagnosis by PrEP modality
    - in the 6 months preceding PrEP initiation
    - during the first period of PrEP use
  - c) Describe the proportion of diagnosed STI with a relevant antimicrobial prescription
- 3.6- Among CAB LA PrEP users diagnosed with HIV (during CAB LA PrEP use or after CAB LA PrEP discontinuation)
- a) Describe the timing of incident HIV diagnoses relative to timing of CAB LA PrEP usage and testing for HIV
  - b) Describe adherence to PrEP injection schedule, HIV treatment, virologic suppression, concomitant STI diagnosis, and HIV drug resistance

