Objective 1b - Among Veterans with a new HIV diagnosis during the study period	Index date	Date of HIV diagnosis
	Censoring criteria	NA
	Endpoint	PrEP use (never, use within 12 months before diagnosis, use >12 months before diagnosis)
Objective set 2 – among Veterans without evidence of HIV infection who are not on PrEP but could benefits from PrEP	Population/exposure	At least one of the following criteria: tested for or diagnosed with a bacterial STI in the past 12 months (gonorrhea, syphilis, chlamydia), tested for HIV in the past 12 months, ever had alcohol use disorder, ever used illicit non-injection drugs, ever used injectable drugs, Black women, men who have sex with men, individuals aged 18-24 years, any history of PrEP use
	Index date	First visit during the study period with criteria indicating the individual could benefit from PrEP
	Censoring criteria	Death, loss to follow-up, end of the study period, 12 months after index date, PrEP initiation, whatever comes first
	Endpoints	HIV testing, HIV diagnosis, Screening/testing for other STIs, STI diagnoses
Objective set 3 – among Veterans with a PrEP prescription	Exposure groups	Oral PrEP, CAB LA PrEP
	Index date	Start of first PrEP regimen during the study period (dispensing date for oral PrEP, injection date for CAB LA)
	Censoring criteria for calculation of proportion of days covered	Death, loss to follow-up (12 months after last clinical contact), study end, 12 months after index date whatever comes first
	Endpoints	Adherence to PrEP schedule, discontinuation and resumption of PrEP, STI screening/testing, STI diagnosis, STI treatment prescription, HIV testing and diagnosis

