**b) CAB LA PrEP: among complete initiators with at least one maintenance injection**

- Total number maintenance injections administered during first period of CAB LA PrEP use (overall and by person)

- Total follow-up time for complete CAB LA initiators with at least one maintenance injection (from first CAB LA PrEP injection to study end, loss to follow-up, death or HIV acquisition, whatever comes first)
- Discontinuation: number of individuals discontinuing CAB LA PrEP and number of individuals resuming LA PrEP injections (additional CAB LA or LEN LA injections after discontinuation and time between the last injection prior discontinuation and the first injection post-discontinuation) or oral PrEP
- Oral bridging between discontinuation of CAB LA injections and resumption of CAB LA injections
- Months on regimen until first censoring (first period of CAB LA PrEP use)  
Calculated as: days from first initiation injection to censoring (study end, loss to follow-up, death, HIV acquisition, discontinuation)
- Cumulative months on regimen across all CAB LA PrEP use (including additional injections after discontinuation)
  - Continuous time on CAB LA PrEP will be calculated as:
    - If no discontinuation: days from first initiation injection to censoring (study end, loss to follow-up, death, HIV acquisition)
    - If discontinuation: days from first initiation injection to discontinuation date (i.e., 127 days after last injection)
  - Among individuals with additional injections after discontinuation, the cumulative months on CAB LA regimen will be calculated across all episodes of continuous CAB LA PrEP use
  - Individuals with incomplete initiation of their first period of CAB LA PrEP use will be excluded from this analysis even if they have additional injections after incomplete initiation
- On CAB LA PrEP at timepoints of interest – among CAB LA users with no discontinuation and among CAB LA users with discontinuation
  - 12 months: injection received between  $\geq 238$  to  $\leq 365$  days after index (up to 127 days before the 12-month mark)
  - 24 months: injection received between  $\geq 603$  to  $\leq 730$  days after index (up to 127 days before the 24-month mark)
  - Study end: injection received up to 127 days before or on study end date
- ◆ **HIV testing & STI testing/screening during first period of PrEP use (Objectives 3.5)**
  - HIV testing

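### The observation period for proportion of days covered does not stop at HIV diagnosis, so days after a first-year diagnosis count as uncovered (minor)

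*Protocol*

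**What the plan says.** Section 7.3.3 (Adherence, Objective 3.3, part b) sets the CAB LA measure as the "Proportion of days covered by CAB LA PrEP in the 12 months following initiation", calculated as the "number of days covered by CAB LA PrEP divided by the number of days in the observation period". The list introduced by "Follow-up will be censored at first of" has four entries: 12 months after index, loss to follow-up, death and study end. Part a) uses the same four for oral PrEP, where the measure is the "Proportion of days of access to oral PrEP in the 12 months following index PrEP initiation". Table 2 in section 7.1 repeats them for Objective set 3: "Death, loss to follow-up (12 months after last clinical contact), study end, 12 months after index date whatever comes first". HIV diagnosis is in none of the three lists.

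For Objective 3.4, the same section calculates months on the CAB LA regimen in the first period of use as "days from first initiation injection to censoring (study end, loss to follow-up, death, HIV acquisition, discontinuation"). Total follow-up time for these users also stops at HIV acquisition.

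Objective 3.6 b) in section 6 concerns CAB LA users diagnosed with HIV and includes: "Describe adherence to PrEP injection schedule, HIV treatment, virologic suppression".

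**The concern.** Section 5 describes PrEP as antiretroviral use by HIV-negative people. After an HIV diagnosis there is no further PrEP day to cover, yet the written rule leaves those days in the denominator. The outcome itself then lowers the coverage value.

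Loss to follow-up does not remove these days. Table 2 places it 12 months after the last clinical contact, so it cannot fall earlier than 12 months after the index date.

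The cases affected are those for whom the distinction matters most: whether infection occurred despite coverage or after coverage had lapsed. Coverage is the first measure listed under adherence to the CAB LA schedule. If that figure were carried into the description of Objective 3.6 cases, a user covered on every day before diagnosis would show a low value.

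**Working it through.** The protocol states no expected coverage value, so there is no figure of its own to reproduce. Its day-count rule can be applied directly.

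**Inputs from section 7.3.3**
- First injection: "coverage = 37 days (30 days of coverage + 7-day injection window").
- Each later injection: 60 + 7 = 67 days.
- Each calendar day is counted once.
- Window: 12 months, taken as 365 days.

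**Assumptions not in the protocol**
- Injections on days 0, 30, 90, 150, 210, 270 and 330, all on time.
- No injection on or after the day of diagnosis.
- Diagnosis day varied.
- The full 12 months falls before study end. For later initiators study end shortens the denominator, and the effect is smaller.

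**Formula.** With k ≥ 2 injections, the last is on day 30 + 60(k − 2), and there is no gap before it. Covered days = 30 + 60(k − 2) + 67 = 60k − 23, capped at 365. As written, coverage = covered days / 365. If observation also ends at diagnosis, every observed day is covered and the value is 100%.

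| Diagnosis day | Injections (k) | Covered days | As written | Censored at diagnosis |
|---|---|---|---|---|
| 90 | 2 | 97 | 97/365 = 26.6% | 90/90 = 100% |
| 120 | 3 | 157 | 157/365 = 43.0% | 120/120 = 100% |
| 180 | 4 | 217 | 217/365 = 59.5% | 180/180 = 100% |
| 240 | 5 | 277 | 277/365 = 75.9% | 240/240 = 100% |
| 330 | 6 | 337 | 337/365 = 92.3% | 330/330 = 100% |
| 360 | 7 | 365 (capped) | 365/365 = 100% | 360/360 = 100% |

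**Check with the latest on-time days** (second injection on day 37, then every 67 days). Diagnosis on day 104, 171, 238 or 305, before that day's injection, gives 104/365 = 28.5%, 171/365 = 46.8%, 238/365 = 65.2% or 305/365 = 83.6%. Each is 100% if censored at diagnosis.

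**Comparison with a late user.** Take an HIV-free user with a second injection on day 37 and every maintenance injection 97 days after the one before, so on days 134, 231 and 328. Table 3 classes each of these as late. Covered days are 104 + 67 + 67 + 37 = 275, and 275/365 = 75.3%. That exceeds the 59.5% of the on-time user diagnosed on day 180.

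**Cohort effect.** One case diagnosed on day 150 (157 covered days) lowers the mean of 748 CAB LA users by (1 − 157/365)/748 = 0.00076, or about 0.08 percentage points. Ten such cases lower it by about 0.8 points. The planned summary is a median, which would barely move.

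**The case against.** The strongest reply is that nothing ties Objective 3.6 to this measure. Section 7.7.1.1 plans an individual timeline for each diagnosed CAB LA user, with injections received and HIV tests performed, so on-time injections before diagnosis stay visible. The completeness-of-initiation categories and Table 3 classify intervals between injections and do not use this denominator. This stands. A reader might infer that the rule would reverse the interpretation of each first-year case; the documents do not support that.

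A reader might also infer that such a Veteran is classed as poorly adherent. The protocol sets no coverage cut-off and no adherence category based on coverage, so the result is only a low percentage. Nor does coverage itself run on: the denominator does, while coverage ends with the last injection's allotted days.

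It can further be said that time on regimen and coverage are different quantities. Time on regimen also stops at discontinuation, and coverage rightly does not, because a fixed-window figure is meant to show access lost by stopping. That is fair, and the Objective 3.4 rule is therefore not a direct contradiction. But stopping PrEP while HIV-negative and leaving the HIV-negative population are different events, and the protocol gives no reason to count the second as lost access.

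Finally, Objective 3.6 covers CAB LA users only, so for oral PrEP the case rests on consistency of definition, with no comparable use at stake.

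**Conclusion.** The point holds as a minor defect in a stated rule. Followed literally, the rule lowers the coverage value of anyone diagnosed in roughly the first 11 months because of the diagnosis itself. For an on-time CAB LA user the value is 26.6% to 75.9% instead of 100% for diagnoses between days 90 and 240. It is 92.3% at day 330 and unaffected from about day 360.

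This rests on PrEP stopping at diagnosis, which is inferred from section 5, and on the assumed injection and diagnosis days. The protocol gives no expected number of first-year diagnoses.

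The cohort median, the interval-based timing measures and the Objective 3.6 timelines are not materially affected. The distortion matters only where the coverage figure is used to describe adherence in CAB LA users diagnosed in their first year.

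**What to change.** Add HIV diagnosis as a censoring event for the proportion of days covered in three places: the Objective set 3 row of Table 2, and the oral and CAB LA lists under Objective 3.3 in section 7.3.3. If coverage is reported for Objective 3.6 cases, calculate it from index to the diagnosis date. If the sponsor prefers a fixed 12-month window regardless of HIV status, the protocol should say so, give the reason, and state that the figure is not to be read as adherence in diagnosed cases.

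The cost is three short wording edits. No new data are needed, because HIV diagnosis is already an endpoint for this cohort and its date is needed for the Objective 3.6 timelines.
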